8.2.2. Withdrawal of Informed Consent

- If the participant withdraws consent for disclosure of future information, the sponsor may retain and continue to use any data collected before such a withdrawal of consent.
- If a participant withdraws from the study, he/she may request destruction of any samples taken and not tested, and the investigator must document this in the site study records.
- Refer to the SoA for data to be collected at the time of study discontinuation and follow-up and for any further evaluations that need to be completed.

8.3. Lost to Follow Up

A participant will be considered lost to follow-up if he or she repeatedly fails to return for scheduled visits and is unable to be contacted by the study site.

The following actions must be taken if a participant fails to return to the clinic for a required study visit:

- The site must attempt to contact the participant and reschedule the missed visit as soon as possible and counsel the participant on the importance of maintaining the assigned visit schedule and ascertain whether or not the participant wishes to and/or should continue in the study.
- Before a participant is deemed lost to follow up, the investigator or designee must make every effort to regain contact with the participant (where possible, 3 telephone calls and, if necessary, a certified letter to the participant's last known mailing address or local equivalent methods). These contact attempts should be documented in the participant's medical record.

Should the participant continue to be unreachable, he/she will be considered to have withdrawn from the study with a primary reason of lost to follow-up

9. STUDY ASSESSMENTS AND PROCEDURES

- Study procedures and their timing are summarized in the SoA (Section 2)
- Protocol waivers or exemptions are not allowed
- Immediate safety concerns should be discussed with the sponsor immediately upon occurrence or awareness to determine if the participant should continue or discontinue study treatment.
- Adherence to the study design requirements, including those specified in the SoA, is essential and required for study conduct.

- All screening evaluations must be completed and reviewed to confirm that potential participants meet all eligibility criteria. The investigator will maintain a screening log to record details of all participants screened and to confirm eligibility or record reasons for screening failure, as applicable. Sites will follow the HIV testing algorithm for Screening detailed in [Appendix 9](#) and included in the SRM. If a reactive/positive result is obtained for any HIV test, the person is not eligible for the study. Additional testing to confirm suspected HIV infection during Screening will be performed in accordance. Participants with reactive screening tests for HIV will receive counselling and be referred for further testing and appropriate management.
- Procedures conducted as part of the participant's routine clinical management (e.g., blood count) and obtained before signing of Informed consent form (ICF) may be utilized for screening or baseline purposes provided the procedure met the protocol-specified criteria and was performed within the time frame defined in the SoA ([Table 1](#)).
 - The maximum amount of blood collected from each participant over the duration of the study, including any extra assessments that may be required, will not exceed 1500 mL.
 - Repeat or unscheduled samples may be taken for safety reasons or for technical issues with the samples.

9.1. Efficacy Assessments

In this study only pharmacokinetic and safety parameters will be evaluated, efficacy assessment is not applicable.

9.2. Adverse Events

The definitions of an AE or SAE can be found in [Appendix 4](#).

The investigator and any designees are responsible for detecting, documenting, and reporting events that meet the definition of an AE or SAE and remain responsible for following up AEs that are serious, considered related to the study treatment or the study, or that caused the participant to discontinue the study treatment (see [Section 8](#)).

Seizures or suspected seizures are to be reported to GSK promptly (within 24 hours of learning of the event) for evaluation and possible onward reporting (see [Section 3.3.2](#)). Any seizures and suspected seizures that meet the definition of an AE or SAE should be reported in these forms.

9.2.1. Time Period and Frequency for Collecting AE and SAE Information

- All SAEs will be collected from the signing of the ICF until the final follow-up visit at the time points specified in the SoA ([Section 2](#)).
- All AEs will be collected from the start of treatment until the final follow-up visit at the time points specified in the SoA ([Section 2](#)).

- Medical occurrences that begin before the start of study treatment but after obtaining informed consent will be recorded on the Medical History/Current Medical Conditions section of the case report form (CRF) not the AE section, unless it is an SAE.
- All SAEs will be recorded and reported to the sponsor or designee immediately and under no circumstance should this exceed 24 hours, as indicated in [Appendix 4](#). The investigator will submit any updated SAE data to the sponsor within 24 hours of it being available.
- Investigators are not obligated to actively seek AEs or SAEs in former study participants. However, if the investigator learns of any SAE, including a death, at any time after a participant has been discharged from the study, and he/she considers the event to be reasonably related to the study treatment or study participation, the investigator must promptly notify the sponsor.
- The method of recording, evaluating, and assessing causality of AE and SAEs and the procedures for completing and transmitting SAE reports are provided in [Appendix 4](#).

9.2.2. Method of Detecting AEs and SAEs

Care will be taken not to introduce bias when detecting AE and/or SAE. Open-ended and non-leading verbal questioning of the participant is the preferred method to inquire about AE occurrence. Appropriate questions include:

- “How are you feeling?”
- “Have you had any (other) medical problems since your last visit/contact?”
- “Have you taken any new medicines, other than those provided in this study, since your last visit/contact?”

9.2.3. Follow-up of AEs and SAEs

After the initial AE/SAE report, the investigator is required to proactively follow each participant at subsequent visits/contacts. All SAEs, and non-serious AEs of special interest (as defined in Section 12.4), will be followed until the event is resolved, stabilized, otherwise explained, or the participant is lost to follow-up (as defined in Section 8.3). Further information on follow-up procedures is given in [Appendix 4](#).

9.2.4. Regulatory Reporting Requirements for SAEs

- Prompt notification by the investigator to the sponsor of a SAE is essential so that legal obligations and ethical responsibilities towards the safety of participants and the safety of a study treatment under clinical investigation are met.
- The sponsor has a legal responsibility to notify both the local regulatory authority and other regulatory agencies about the safety of a study treatment under clinical investigation. The sponsor will comply with country-specific regulatory requirements relating to safety reporting to the regulatory authority,

Institutional Review Boards (IRB)/Independent Ethics Committees (IEC), and investigators.

- Investigator safety reports must be prepared for suspected unexpected serious adverse reactions (SUSAR) according to local regulatory requirements and sponsor policy and forwarded to investigators as necessary.
- An investigator who receives an investigator safety report describing a Serious adverse event (SAE) or other specific safety information (e.g., summary or listing of SAE) from the sponsor will review and then file it along with the Investigator's Brochure and will notify the IRB/IEC, if appropriate according to local requirements.

9.2.5. Cardiovascular and Death Events

For any cardiovascular events detailed in [Appendix 4](#) and all deaths, whether or not they are considered SAEs, specific Cardiovascular (CV) and Death sections of the CRF will be required to be completed. These sections include questions regarding cardiovascular (including sudden cardiac death) and non-cardiovascular death.

The CV CRFs are presented as queries in response to reporting of certain CV Medical Dictionary for Regulatory Activities (MedDRA) terms. The CV information should be recorded in the specific cardiovascular section of the CRF within one week of receipt of a CV Event data query prompting its completion.

The Death CRF is provided immediately after the occurrence or outcome of death is reported. Initial and follow-up reports regarding death must be completed within one week of when the death is reported.

9.3. Treatment of Overdose

For the Oral Phase of this study, any dose of CAB greater than 1 tablet (30 mg) within a day will be considered an overdose. For the Injection Phase, any dose of CAB LA greater than 600 mg will be considered an overdose. GSK does not recommend specific treatment for an overdose. The investigator will use clinical judgment to treat any overdose. In the event of an overdose, the investigator or treating physician should:

1. Contact the Medical Monitor immediately.
2. For oral overdose, closely monitor the participant for AE/SAE and laboratory abnormalities (at least 14 days). For injection overdose monitor the participant for AE/SAE and laboratory abnormalities as per the SoA.
3. For oral overdose, obtain a plasma sample for PK analysis within 14 days from the date of the last dose of study treatment if requested by the Medical Monitor (determined on a case-by-case basis).
4. Document the quantity of the excess dose as well as the duration of the overdosing in the CRF.

Decisions regarding dose interruptions or modifications will be made by the investigator in consultation with the Medical Monitor based on the clinical evaluation of the participant.

9.4. Safety Assessments

Planned time points for all safety assessments are provided in the SoA (Section 2).

9.4.1. Physical Examinations

- A complete physical examination will include, at a minimum, assessment of the (Skin, Cardiovascular, Respiratory, Gastrointestinal and Neurological) systems. Height and weight will also be measured and recorded.
- A brief physical examination will include, at a minimum assessments of the (Skin, lungs, cardiovascular system, and abdomen [Liver and spleen]).
- Investigators should pay special attention to clinical signs related to previous serious illnesses.

9.4.2. Injection site reaction

Injection site reactions will be recorded via ISR diaries and managed through investigator assessment throughout the study. All ISRs that are either serious, Grade 3 or higher, or persisting beyond 2 weeks must be discussed with the Medical Monitor to determine etiology and assess appropriate continued study participation. Digital photographs may be documented where possible on all participants who have an injection site reaction, with observable findings, that is either serious or Grade 3 or higher, or that persists beyond 2 weeks. Dermatology will be consulted on all participants who have an injection site reaction considered serious, Grade 3 or above, or if clinically significant and persistent beyond 30 days and others if the Investigator or Medical Monitor feels it is medically necessary. Details regarding photo collection and any other follow up will be given by the Medical Monitor at the time of assessment. ISR discomfort can be managed symptomatically (e.g., cold/warm compress, acetaminophen, ibuprofen) if the reaction is interfering with the participant's ability to perform activities of daily living. The required intervention should be documented on the appropriate eCRF page.

9.4.3. HIV Counseling

Participants will be assessed for HIV risk behaviors at each visit and should be provided with risk-reduction counseling. This should also include assessing sexually transmitted diseases symptoms (testing and treating to be applied, as needed). If a significant change in risk from baseline is identified during the study, the investigator should discuss continuing participation with the medical monitor. Participants with documented risk behaviors requiring the use of PEP should have study treatment withdrawn and managed as per Section 8.2.

9.4.4. Acquisition of HIV During the Study

A participant with a positive POC test will have additional samples collected at the same visit to confirm the acquisition of HIV. A confirmatory test either western blot, HIV ½ Multispot or the Geenius HIV Confirmation ½ Assay, and HIV RNA will be performed. Further information on interpretation is available in the SRM. Participants who become HIV-infected during the course of this study will be referred to care. It is the responsibility of the principal investigator to refer the HIV positive participant to an appropriate center for HIV care. Investigator will guide HIV positive participants to start suppressive HIV treatment as soon as possible to minimize the risk of development of drug resistance. A post-HIV confirmation visit will be scheduled and procedures will be performed as outlined in [Appendix 5](#). Participants who become infected with HIV-1 during the Injection Phase should enter the follow-up phase and be managed as per [Section 8.2](#).

9.4.5. Vital Signs

Vital signs will be measured in a semi-supine position after 5 minutes rest and will include temperature, systolic and diastolic blood pressure, and pulse rate and respiratory rate. Three readings of blood pressure and pulse will be taken. The first reading should be rejected. The second and third readings should be averaged to give the measurement to be recorded in the CRF.

9.4.6. Electrocardiograms

A single 12-lead ECG will be obtained at screening as outlined in the SoA (Section 2) using an ECG machine that automatically calculates the heart rate and measures PR, QRS, QT, and corrected QT interval (QTc) intervals.

9.4.7. Clinical Safety Laboratory Assessments

- Refer to [Appendix 2](#) for the list of clinical laboratory tests to be performed and to the SoA for the timing and frequency.
- The investigator must review the laboratory report, document this review, and record any clinically relevant changes occurring during the study in the AE section of the CRF. The laboratory reports must be filed with the source documents.
- All laboratory tests with values considered clinically significantly abnormal during participation in the study or within 14 days after last dose of oral study treatment or 56 weeks following their last injection, should be repeated until the values return to normal or baseline or are no longer considered significantly abnormal by the investigator or medical monitor.
- If such values do not return to normal/baseline within a period of time judged reasonable by the investigator, the aetiology should be identified and the sponsor notified.

- All protocol-required laboratory assessments, as defined in [Appendix 2](#), must be conducted in accordance with the laboratory manual and the SoA.
- Blood plasma samples for storage will be collected as indicated in the Section 2 (SoA). Stored plasma will also be collected from participants who acquire HIV infection, these assessments include: CAB PK measurements, CD4 count, Viral Load, resistance testing, HIV sub typing, characterization of the virus and/or the host response to infection. As these assessments will be performed retrospectively; results will not be returned to study sites or participants. An HIV confirmatory visit will be scheduled ([Appendix 5](#)).

9.5. Pharmacokinetics

- Intensive oral CAB PK will be measured in approximately 16 subjects. These subjects will spend three continuous nights at the clinic. Subjects will check in on Day 25 and will take the Day 26 oral dose (e.g. 8 AM) at the clinic. Sample collections on Day 27 following oral dose (e.g. 8 AM) at the clinic. Sample collections on Day 27 following observed oral CAB dosing in the clinic will be obtained before oral dose (e.g. 7:55 AM), and following dose administration at 1, 2, 3, 4, 8 -hour post-dose and on Day 28, 24-hour post the Day 27 dose. Approximately 2mL of blood samples will be collected at each of these time points. The last oral dose will be administered on day 28 after the final PK sample with subsequent safety and central lab assessment on the same day. For study subjects not participating in the intensive PK part of the study, they will come in only for day 28 visit for pre-dose PK sampling (approximately 20 to 28 hours after the dose taken at home the day prior) as well as safety and central lab assessment.
- Blood samples will be processed to harvest plasma within 1hr of sample collection. Samples collected for analyses of study treatment, plasma concentration may also be used to evaluate safety or efficacy aspects related to concerns arising during or after the study.
- Determination of CAB concentration in plasma will be performed in Covance Pharmaceutical R&D (Shanghai) Co., Ltd under the monitoring of GlaxoSmithKline. CAB concentrations will be determined in plasma using an approved, validated analytical methodology. A method validation report will be generated to demonstrate the details in validation assessments.
- Once the plasma has been analyzed for CAB, any remaining plasma to be used may be analyzed for other compound-related metabolites and the results reported under a separate protocol.
- All pharmacokinetic analyses will be performed under the direction and supervision of the Antiviral Group of Clinical Pharmacology Modelling and Simulation (CPMS) at GlaxoSmithKline. Individual plasma PK parameters will be determined by non-compartmental methods using WinNonlin Professional 5.2 or higher, Phoenix (Certara Corporation) or comparable software.

- PK parameters following oral administration may include area under the plasma concentration time curve over the dosing interval (AUC [0- τ]), maximum observed concentration (C_{max}), time to maximum observed concentration (t_{max}), concentration at the end of the dosing interval (C _{τ}), oral clearance (CL/F) and steady state volume (V_{ss}). Following CAB LA administration, individual plasma PK parameters for specific injection intervals of the Week 5-41 injection phase of the study will be determined where applicable, and may include: area under the plasma concentration time curve over the dosing interval (AUC [0- τ]), maximum observed concentration (C_{max}), time to maximum observed concentration (t_{max}), concentration at the end of the dosing interval (C _{τ}), and apparent terminal phase half-life for CAB LA administration (t_{1/2}) and lambda z as a measure of absorption rate constant (λ_z) if data allow. Plasma levels of CAB will be measured during the Follow-up phase between weeks 41 to 89 to determine λ_z and t_{1/2} for the final injection interval starting at Week 33.

9.6. Pharmacodynamics

Blood draws are listed in the SoA and Section 9.5 to assess the relationship between drug levels and or the emergence of adverse events (HIV acquisition).

9.7. Genetics

Genetics are not evaluated in this study.

9.8. Biomarkers

Biomarkers are not evaluated in this study

9.9. Health Economics OR Medical Resource Utilization and Health Economics

Health Economics/Medical Resource Utilization and Health Economics parameters are not evaluated in this study

10. STATISTICAL CONSIDERATIONS

10.1. Sample Size Determination

10.1.1. Hypotheses

No formal statistical hypotheses will be evaluated. The study is designed to evaluate the PK, safety, tolerability, and acceptability of the injectable agent, CAB LA (600 mg dose administered at 8-week intervals after 2 initial doses 4 weeks apart) in HIV-uninfected men in China where at least 60% of the men are of a population who have sex with men. Where appropriate, an estimation approach will be taken, and point estimates and confidence intervals will be constructed.

10.1.2. Sample Size Considerations

The sample size of 40 participants given the CAB LA treatment was chosen to ensure an adequate evaluation of safety, tolerability and pharmacokinetics data in this population prior to moving into a large phase 3 study.

10.2. Populations for Analyses

For purposes of analysis, the following populations are defined:

Population	Description
All Subjects Screened Population	The All Subjects Screened Population will include all subjects who consent to participate in the clinical study. Subjects in this population will be used for disposition summary
Safety Population	The Safety Population will include all subjects who receive at least one dose of the study treatment. Subjects in this population will be used for all demographic and safety summaries or listings.
Oral Pharmacokinetic (PK) Population	The Oral PK Population will include those subjects in the Safety population for whom at least one evaluable intensive Oral PK sample will be obtained and analyzed. Oral pharmacokinetic samples that may be affected by protocol deviations will be reviewed by the study team and determined whether the or not the sample will be excluded. All Oral PK analyses will be based on this analysis population.
Injection Pharmacokinetic (PK) Population	The Injection PK Population will include all subjects in the Safety population for whom at least one evaluable Injection PK sample will be obtained and analyzed. Injection pharmacokinetic samples that may be affected by protocol deviations will be reviewed by the study team and determined whether or not the sample will be excluded. All Injection PK analyses will be based on this analysis population.

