- HIV PoC (Point of care) test will be performed at each time point during the course of the study and must be reviewed prior to IM dosing. See [Appendix 9](#) for the HIV testing algorithm at screening, Day 1 and during the course of the study.
- ECGs will be performed following 5 minutes of rest in a semi-supine position.
- Liver Chemistry Tests include Alanine aminotransferase (ALT), Aspartate aminotransferase (AST), Bilirubin total and direct.

- m. Oral Pharmacokinetic (PK) sampling at trough will be collected for all subjects prior to dose within 20 to 28 hours following oral administration the day prior. Intensive oral PK sampling will be collected from approximately 16 participants as shown in [Table 2](#).
- n. PK sampling for Injection phase: All PK samples will be collected prior to CAB LA injections at Week 5, 9, 17, 25, and 33 with the exception of 1-week post injection samples at Weeks 6, 10, 18, 26, 34, week 37(4-week post injection sample) and Week 41
- o. Long-term follow up PK samples: PK sampling during follow up will occur at, Week 53, 65, 77, and 89.
- p. Additional testing is required for participants who have a reactive or positive HIV test after enrolment. Stored plasma from the visit previous to the positive test should be tested for HIV using the 4th generation HIV test to best estimate time of infection. HIV acquisition must be confirmed by either western blot, HIV ½ Multispot or the Geenius HIV Confirmation ½ Assay, and HIV RNA.
- q. Visit may occur in a window ± 3 Days

Table 2 SCHEDULE OF INTENSIVE ORAL PK APPROXIMATELY 16 PARTICIPANTS) ^{a,b}

	Day 25	Day 26	Day 27							Day 28	
	Check-in	Oral dose administered (e.g. 8AM)	Prior to oral dose (e.g. 7:55AM)	Oral dose administered (e.g. 8AM)	1-hour post dose (e.g. 9AM)	2-hour post dose (e.g. 10AM)	3-hour post dose (e.g. 11AM)	4-hour post dose (e.g. 12AM)	8-hour post dose (e.g. 4PM)	24-hour post dose (e.g. 8AM)	Oral dose administered (e.g. after 8 AM)
Plasma for CAB concentration			X		X	X	X	X	X	X	

- a. PK sampling may occur ± 15 min
- b. Central lab tests for the intensive oral PK subjects refer to [Table 1](#).

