Secondary Endpoint	
 Plasma CAB AUC(0-τ), C_{max}, C_{τ}, t_{max}, λ_z, t_{1/2}, CL/F, and Vz/F through Weeks 5-89. Safety and tolerability parameters, including adverse events, study withdrawals due to AEs, vital signs assessments, and clinical laboratory assessments, for oral lead-in phase (Day 1 to Week 4). Injection discontinuation rate, the number and severity of ISRs and additional acceptability measures. Evaluation of relationships between significant safety and tolerability

Overview	Key Elements of the RAP
	parameters and CAB PK may be explored.
Study Design	
 • This will be an open label, non-randomized, single arm study. Participants will receive daily oral CAB (30mg tablets) for 4 weeks during the Oral Phase of the study and intramuscular (IM) injections of 600 mg of CAB LA at Week 5, Week 9, Week 17, Week 25 and Week 33. • Starting at 8 weeks post last injection, participants will be seen once every 12 weeks for 48 weeks during the follow-up phase. • Subjects who volunteer to participate in the intensive PK assessment will have serial blood sampling for measurement of plasma CAB concentrations following oral administration over a 24 h window starting on Day 27 and ending on Day 28 • PK samples at trough for Oral Phase will be collected for all subjects prior to dose within 20 to 28 hours following oral administration the day prior; Intensive oral PK samples will be collected from approximately 16 participants. • PK Samples for Injection Phase will be collected prior to CAB LA injections at Week 5, 9, 17, 25, and 33 with the exception of 1-week post injection samples at Weeks 6, 10, 18, 26, 34, 37 (4-week post injection sample) and Week 41 • Long-term follow up PK samples will be collected at Week 53, 65, 77, and 89.
Planned Analyses	
 • The primary safety analysis and PK analyses including both oral phase and injection phase through Weeks 5 to 41 will be performed after all ongoing participants complete the Week 41 visit or withdraw from the study treatment, whichever comes first. • The end of study analysis will be performed after all ongoing participants complete the Week 89 visit or withdraw from the study treatment, whichever comes first.

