Analysis Populations	
 • The All Subjects Screened Population will include all subjects who consent to participate in the clinical study. Subjects in this population will be used for disposition summary • The Safety Population will include all subjects who receive at least one dose of the study treatment. Subjects in this population will be used for all demographic and safety summaries or listings, as well as for the analysis of acceptability of CAB LA. • Safety Injection Population will include all subjects received at least one CAB LA injection. Subjects in this population will be used to evaluate the safety and tolerability of CAB LA injection in primary analysis. • Oral PK Population: subjects in the 'Safety population' for whom an intensive oral pharmacokinetic sample was obtained and analysed. PK samples that may be affected by protocol deviations will be reviewed by the study team to determine whether or not the sample will be excluded. This population will be used for reporting of Oral PK data.

Overview	Key Elements of the RAP
	
 ● Injection (Week 41) PK Population: subjects in the 'Safety population' for whom an injection pharmacokinetic sample was obtained and analysed during Weeks 5 to 41. PK samples that may be affected by protocol deviations will be reviewed by the study team to determine whether or not the sample will be excluded. This population will be used for reporting of Injection PK data from Weeks 5 to 41. ● Injection (Week 89) PK Population: subjects in the 'Safety population' for whom an injection pharmacokinetic sample was obtained and analysed during Weeks 5 to 89. PK samples that may be affected by protocol deviations will be reviewed by the study team to determine whether or not the sample will be excluded. This population will be used for reporting of Injection PK data from Weeks 5 to 89.
Hypothesis	
 ● No formal statistical hypotheses will be evaluated.

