4. ANALYSIS POPULATIONS

Population	Definition / Criteria	Analyses Evaluated
All Subjects Screened	
 Comprise of all subjects who consent to participate in the clinical study. 	
 Disposition summary
Safety	
 Comprise of all subjects who receive at least one dose of the study treatment. 	
 All demographic General safety analyses Safety analysis for the oral phase Analysis of acceptability of CAB LA
Safety Injection	
 Comprise of all subjects received at least one CAB LA injection 	
 Safety and tolerability analyses of CAB LA in primary and extended analyses
Oral Pharmacokinetic (PK)	
 Will consist of all subjects in the 'Safety population' for whom an intensive oral pharmacokinetic sample was obtained and analysed. PK samples that may be affected by protocol deviations will be reviewed by the study team to determine whether or not the sample will be excluded. 	
 Oral PK Concentration Oral PK Parameters
Injection (Week 41) Pharmacokinetic (PK)	
 Will consist of all subjects in the 'Safety population' for whom an injection pharmacokinetic sample was obtained and analysed during Weeks 5 to 41. PK samples that may be affected by protocol deviations will be reviewed by the study team to determine whether or not the sample will be excluded. 	
 Injection PK Concentration Injection PK Parameters
Injection (Week 89) Pharmacokinetic (PK)	
 Will consist of all subjects in the 'Safety population' for whom an injection pharmacokinetic sample was obtained and analysed during Weeks 5 to 89. PK samples that may be affected by protocol deviations will be reviewed by the study team to determine whether or not the sample will be excluded. 	
 Injection PK Concentration Injection PK Parameters

NOTES:

Please refer to [Appendix 14](#): List of Data Displays which details the population to be used for each display being generated.

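### Every participant is scheduled to give a Day 28 oral trough, but all itemised oral PK displays use a population that requires an intensive sample, so about 24 to 32 participants' troughs are not summarised or listed

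*Protocol*

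**What the plan says.** **Collection.** Footnote m to the protocol's schedule of activities states: "Oral Pharmacokinetic (PK) sampling at trough will be collected for all subjects prior to dose", 20 to 28 hours after the previous day's dose. The SAP synopsis agrees: "PK samples at trough for Oral Phase will be collected for all subjects prior to dose". Protocol 9.5 says of participants outside the intensive group that "they will come in only for day 28 visit for pre-dose PK sampling", so this is their only oral-phase PK sample. Intensive sampling over 24 hours is planned in about 16 volunteers.

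**Analysis.** Protocol 10.2 restricts the Oral PK population to Safety participants "for whom at least one evaluable intensive Oral PK sample will be obtained and analyzed" and adds: "All Oral PK analyses will be based on this analysis population". SAP section 4 uses the same restriction ("for whom an intensive oral pharmacokinetic sample was obtained and analysed"), and the SAP synopsis says: "This population will be used for reporting of Oral PK data". Oral Cτ is among the primary PK endpoints (Protocol section 4, SAP 2.2).

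**A sentence that points the other way.** Protocol 10.3.1.2 says that concentration-time summaries will use all data for each planned visit, whatever the actual timing, and separately the data inside the allowed windows. Day 28 is a planned PK visit for everyone.

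**The concern.** Limiting AUC(0-τ), Cmax and terminal-phase parameters to the intensive group is a stated design choice and is not disputed: those parameters need a profile. The trough does not. SAP Table 10 takes Cτ directly from the observed concentration at the end of the dosing interval, and a single pre-dose sample approximates that value.

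The population rule nevertheless removes the single troughs along with everything else. Blood is drawn from every participant for a measurement that belongs to a primary objective, and the plan then itemises no summary and no listing of it for the majority. What is at stake is how precisely and completely the oral trough is described in this population. The remaining description also rests on volunteers for an in-clinic stay.

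**Working it through.** **1. Trace each PK display in SAP Appendix 14 to its population.**

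| Displays | Population | Non-intensive Day 28 troughs? |
|---|---|---|
| Tables 3.1–3.3, Figures 3.1–3.2, Listings 39–40 (oral phase) | Oral PK | No: intensive sample required |
| Tables 3.4–3.8, Figures 3.3–3.6, Listings 41–42 | Injection (Week 41) PK | No: injection-phase data |
| Tables 3.9–3.11, Figures 3.7–3.8, Listings 43–44 | Injection (Week 89) PK | No: injection-phase data |
| Non-ICH listings (10.14.11) | none itemised | No |

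The Week 41 injection population is defined by participants "for whom an injection pharmacokinetic sample was obtained and analysed during Weeks 5 to 41". Under SAP 10.4.1 the oral phase runs to the day before the first injection, so Day 28 is oral-phase data. The note on Listing 39 to include all concentrations, unscheduled ones too, operates within the Oral PK population. The older plan text contained in the same SAP file gives the same definitions and display populations.

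**2. Count the participants affected.** Protocol 5.2 gives about 48 entering the oral phase and about 40 entering the injection phase. Between 40 (all oral-phase dropouts leave before Day 28) and 48 (none do) should have a Day 28 trough.

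- 40 − 16 = 24 (60%)
- 48 − 16 = 32 (67%)

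**3. Precision if the log-scale SD is the same in both groups.** The documents give no precision target and no CV for oral Cτ, so there is no plan figure to reproduce. The half-width of the 95% interval for a log-scale mean is t(0.975, n−1)/√n × s, with s = √ln(1+CV²).

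- n = 16: 2.131/√16 = 0.5329
- n = 40: 2.023/√40 = 0.3198
- n = 48: 2.012/√48 = 0.2904

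Ratios: 0.5329/0.3198 = 1.67 and 0.5329/0.2904 = 1.84. Under equal s these do not depend on the CV. Absolute limits do, so the CV below is an assumption. Upper 95% limit as a multiple of the geometric mean:

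| Assumed CV | n = 16 | n = 40 | n = 48 |
|---|---|---|---|
| 30% | 1.17 | 1.10 | 1.09 |
| 40% | 1.23 | 1.13 | 1.12 |
| 60% | 1.34 | 1.19 | 1.17 |

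**4. Allow for unobserved prior doses.** Protocol 5.5 gives geometric mean oral Cmax 7.5 and Cτ 4.2 µg/mL. Assume that this fall takes 20 to 23 h: k = ln(7.5/4.2)/20 = 0.0290 per h, or ln(7.5/4.2)/23 = 0.0252 per h.

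- A missed prior dose shifts the log trough by d = 24k = 0.696 or 0.605, a fall of 50% or 45%.
- A 4 h shift within the 20–28 h window moves one trough by about 10–12%: exp(±4k) = 1.12 and 0.89, or 1.11 and 0.90.

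Assume that 10% of non-intensive participants missed that dose unrecorded. As a share of all participants, q = 0.10 × 24/40 = 0.060, or 0.10 × 32/48 = 0.067.

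- Bias in the geometric mean, exp(−dq) − 1: −3.6% to −4.1% (n = 40); −4.0% to −4.5% (n = 48).
- Added log-scale variance, d²q(1−q): 0.021 to 0.027 (n = 40); 0.023 to 0.030 (n = 48). At CV 30%, s² = 0.086, so the SD rises by a factor of 1.11 to 1.15 (n = 40) or 1.12 to 1.16 (n = 48).
- Ratio of interval widths at CV 30%: 1.67 becomes about 1.45–1.50, and 1.84 becomes about 1.58–1.63. At CV 40% the ratios are 1.53–1.56 and 1.67–1.71.

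**The case against.** **The protocol already promises a summary of all data.** Protocol 10.3.1.2 can be read that way. But 10.2 places every oral PK analysis on the restricted population, and the SAP follows 10.2. The sentence does not rescue the troughs; it creates a conflict to resolve.

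**The display list is incomplete.** This stands. SAP 10.14.1 announces Listings 1–51 and Safety Tables 2.1–2.32, but only Listings 1–44 and Tables up to 2.29 are itemised, and display specifications are available only on request. A reader might infer that no display of these troughs will exist at all. The documents support only that none is itemised.

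**The samples have other uses.** Also true. Protocol 9.5 allows concentrations to be used for safety questions, Appendix 6 matches PK samples to liver findings, SAP 3.1 plans an informal PK review after the oral phase, and Protocol 10.3.5 reports a population PK analysis separately. It would be wrong to infer that the troughs cannot be inspected. None of these is a planned summary of the oral trough, and none names these samples.

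**Other oral-derived concentrations are reported.** The Week 5 pre-injection sample, 7 days after the last oral dose, falls in the Week 41 injection population. One therefore cannot say that only the intensive group has any oral-derived concentration reported. That sample is a washout value, not a steady-state trough.

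**The larger sample is not a cleaner estimate of Cτ.** This is the strongest point. The extra troughs follow unobserved home doses and a wide window, so they approximate the 24 h value. Reporting them beside the supervised Cτ leaves the precision of the supervised estimate unchanged, and the gain of 1.67 to 1.84 cannot be claimed unconditionally.

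**Conclusion.** The point holds as an internal inconsistency and a completeness gap: troughs are scheduled for everyone, while every itemised oral PK display leaves out roughly 24 to 32 participants, and Protocol 10.2 and 10.3.1.2 disagree about whether that is intended. The count rests on approximate targets (16, 40, 48); oral-phase dropouts may be replaced, so the actual number may differ.

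On precision, the interval at n = 16 is 1.67 times (n = 40) to 1.84 times (n = 48) wider, provided the log-scale SD is equal in supervised and unsupervised troughs. With 10% unrecorded missed prior doses and CV 30%, both assumptions, the ratio is about 1.45–1.50 and 1.58–1.63, with about 4% downward bias.

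A reader might take this as a threat to the primary PK result. The documents do not support that: no hypothesis is tested, the modelled PK analyses concern the injection phase only, and steady-state oral parameters were assigned to the intensive group by design. No decision changes. Severity: minor completeness improvement.

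**What to change.** - Reconcile Protocol 10.2 with 10.3.1.2, stating which population the Day 28 oral trough is summarised on.
- Define an oral trough population in the SAP: Safety participants with an evaluable Day 28 pre-dose sample (about 40 to 48).
- Summarise and list the Day 28 trough on that population, showing actual time since the previous dose in the listing. Present it as a supportive result beside the supervised Cτ from the intensive subset, with each clearly labelled.
- Keep AUC(0-τ), Cmax, tmax, CL/F and terminal-phase parameters on the intensive subset.
- Align the announced and itemised display numbers in SAP Appendix 14.

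The cost is one population definition, one concentration summary and one extended listing, with no new samples or assays. The downside is that prior doses outside the clinic are unobserved and the window is 20–28 h. Pill counts, the oral diary card and the tablet record can flag some missed doses; the supervised estimate alongside shows whether the two differ materially.
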